13.1 Regulatory and ethical compliance

This clinical study was designed and shall be implemented, executed and reported in accordance with the ICH Harmonized Tripartite Guidelines for Good Clinical Practice, with applicable local regulations (including European Directive 2001/20/EC, US CFR 21), and with the ethical principles laid down in the Declaration of Helsinki.

13.2 Responsibilities of the investigator and IRB/IEC

Before initiating a trial, the investigator/institution must obtain approval/favorable opinion from the Institutional Review Board/Independent Ethics Committee (IRB/IEC) for the trial protocol, written informed consent form, consent form updates, participant recruitment procedures (e.g. advertisements) and any other written information to be provided to participants. Prior to study start, the investigator is required to sign a protocol signature page confirming his/her agreement to conduct the study in accordance with these documents and all of the instructions and procedures found in this protocol and to give access to all relevant data and records to Novartis monitors, auditors, Novartis Quality Assurance representatives, designated agents of Novartis, IRBs/IECs, and regulatory authorities as required. If an inspection of the clinical site is requested by a regulatory authority, the investigator must inform Novartis immediately that this request has been made.

13.3 Publication of study protocol and results

The study will be registered in a publicly accessible database such as clinicaltrials.gov and as required in EudraCT. In addition, after study completion (defined as last participant last visit) and finalization of the study report, the results and the protocol of this trial will be submitted for publication and posted in a publicly accessible database of clinical trial results, such as the Novartis clinical trial results website and all required Health Authority websites (e.g. Clinicaltrials.gov, EudraCT etc.).

For details on the Novartis publication policy including authorship criteria, please refer to the Novartis publication policy training materials that were provided to you at the trial investigator meetings.

13.4 Quality Control and Quality Assurance

Novartis maintains a robust Quality Management System (QMS) that includes all activities involved in quality assurance and quality control, to ensure compliance with written Standard Operating Procedures as well as applicable global/local GCP regulations and ICH Guidelines.

Audits of investigator sites, vendors, and Novartis systems are performed by auditors, independent from those involved in conducting, monitoring or performing quality control of the clinical trial. The clinical audit process uses a knowledge/risk based approach.

Audits are conducted to assess GCP compliance with global and local regulatory requirements, protocols and internal SOPs, and are performed according to written Novartis processes.

14 Protocol adherence

This protocol defines the study objectives, the study procedures and the data to be collected on study participants. Additional assessments required to ensure safety of participants should be administered as deemed necessary on a case by case basis. Under no circumstances including incidental collection is an investigator allowed to collect additional data or conduct any additional procedures for any purpose involving any investigational drugs under the protocol, other than the purpose of the study. If despite this interdiction prohibition, data, information, observation would be incidentally collected, the investigator shall immediately disclose it to Novartis and not use it for any purpose other than the study, except for the appropriate monitoring on study participants.

Investigators ascertain they will apply due diligence to avoid protocol deviations. If an investigator feels a protocol deviation would improve the conduct of the study this must be considered a protocol amendment, and unless such an amendment is agreed upon by Novartis and approved by the IRB/IEC and Health Authorities, where required, it cannot be implemented.

16.1 Appendix 1: Liver event and laboratory trigger definitions & follow-up requirements

Table 16-1 Liver event and laboratory trigger definitions

	Definition/ threshold

Liver laboratory triggers
 
If ALT, AST and total bilirubin normal at baseline:
	
 • ALT or AST > 5 × ULN • ALP > 2 × baseline (in the absence of known bone pathology) • Total bilirubin > 3 × ULN (in the absence of known Gilbert syndrome) • Potential Hy's Law cases (defined as ALT or AST ≥ 3 × ULN and Total bilirubin ≥ 2 × ULN [> 50% conjugated fraction] with no initial findings of cholestasis (i.e. ALP < 2 × ULN at baseline) and a hepatocellular pattern of injury at the time of liver injury (R ratio ≥ 5)*) • Any clinical event of jaundice (or equivalent term) • ALT or AST > 3 × ULN accompanied by (general) malaise, fatigue, abdominal pain, nausea, or vomiting, or rash with eosinophilia • Any adverse event potentially indicative of a liver toxicity
If ALT or AST abnormal at baseline:	
 • ALT or AST > 2x baseline or > 300 U/L (whichever occurs first)
*R ratio: ALT / ALP, using factor of elevation over ULN for both enzymes	

Table 16-2 Follow-up requirements for liver laboratory triggers and liver symptoms

ALT	TBL	Liver Symptoms	Action
ALT increase without bilirubin increase post dose:			
If normal at baseline: ALT > 5 x ULN If elevated at baseline: ALT > 3 x baseline	Normal TBL OR If TBL elevated at baseline : no change from baseline TBL	None	
 • No change to study treatment • Measure ALT, AST, ALP, TBIL, DBIL, INR, albumin and LDH within 48 hours and at least 1x per week thereafter until resolved • Follow-up for symptoms • Initiate close monitoring and workup for competing etiologies
ALT > 20x ULN	Normal	None	
 • Discontinue IV cipargamin and switch to IV artesunate • Continue IV artesunate based on benefit risk assessment of the investigator • Report as SAE • Measure ALT, AST, ALP, TBIL, INR, albumin and LDH in 48 hours and at least 1x per week thereafter until resolved • Follow-up for symptoms • Initiate close monitoring and workup for competing etiologies

ALT	TBL	Liver Symptoms	Action
ALT increase with bilirubin increase post dose:			
If normal at baseline: ALT > 3 x ULN If elevated at baseline: ALT > 3 x baseline	TBL ≥ 2 x baseline AND ≥ 2 x ULN AND at least doubling of conjugated (=direct) bilirubin from baseline	None	
 • Discontinue IV cipargamin and switch to IV artesunate • Continue IV artesunate based on benefit risk assessment of the investigator • Report as SAE • Measure ALT, AST, ALP, TBIL, INR, albumin and LDH in 48 hours and at least 1x per week thereafter until resolved. • Follow-up for symptoms. • Initiate close monitoring and workup for competing etiologies.

Actions related to liver events and laboratory triggers:

- Repeat liver chemistry tests should be performed using the local laboratory used by the site. Test results must be reported as appropriate.
- Hospitalization of the participant if appropriate
- Causality assessment of the liver event
- Thorough follow-up of the liver event should include
 - investigations based on investigator's discretion: serology tests, imaging (abdominal Ultrasound, CT or MRI as appropriate) and pathology assessments,
 - hepatologist's consult,
 - obtaining more detailed history of symptoms and prior or concurrent diseases,
 - obtaining history of concomitant drug use (including nonprescription medications and herbal and dietary supplement preparations), alcohol use, recreational drug use, and special diets
 - exclusion of underlying liver disease

All follow-up information and procedures performed must be recorded as appropriate in the CRF.

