However, overall clinical outcome in severe malaria patients is dependent on the comprehensive case management including supportive treatment. Hence, at least a basic minimum standard of supportive therapy will be maintained across all the sites in this study.

Potential risks with the use of IV cipargamin

Resistance

The risk of developing resistant strains of parasite is low since IV monotherapy will be followed by oral standard of care in all the patients. Any recrudescence or new infection will be managed with standard of care pharmacotherapy that should effectively eliminate any parasites.

Delayed hemolysis

Based on prospective studies delayed hemolysis has been detected in 7-27% of the severe malaria participants treated with IV artesunate ([Rolling et al 2014](#), [Kurth et al 2017](#)). Hyperparasitemia in non-immune travelers and young age in the endemic regions are the confirmed risk factors. The hemolytic event typically peaks 2-3 weeks after the acute phase of malaria. Removal of dead parasites from the erythrocytes in the spleen and leaving behind the "once-infected" erythrocytes, which are characterized by a shorter life span, is one of the assumed mechanism. Based on the mechanism of action of cipargamin, delayed hemolysis might occur also in connection with IV cipargamin therapy. All participants will be followed up closely for at least 4 weeks and given supportive treatment as needed.

Liver safety

Reversible and asymptomatic LFT elevations were observed with 75 mg single dose in a patient study in uncomplicated malaria and with 10 mg single dose in a human challenge study ([Investigator's Brochure](#)). Increase in LFT levels in these studies could have been influenced by the disease condition itself and/or the specific human challenge model ([Chughlay et al 2020](#)). Changes in LFTs are often associated with malaria but liver function generally improves as the patient recovers ([Reuling et al 2018](#), [Woodford et al 2018](#)). In Cohort 1 of the study, participants with ALT > 5 x ULN (regardless the level of total bilirubin) and total bilirubin is > 3 mg/dL will be excluded. In this study, all participants will be closely monitored, including regular liver function tests, and in addition, it will be ensured that all participants would have access to standardized supportive treatment like IV fluid replacement and transfusion.

Semen discoloration

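### Read literally, protocol Table 16-2 stops cipargamin at ALT above 20x ULN when bilirubin is normal, but not when bilirubin was raised at baseline and is unchanged

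*Protocol*

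**What the plan says.** Table 16-2 in protocol Section 16.1 has three rows. All three apply to participants with no liver symptoms.

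- **Row 1.** ALT above 5x ULN if normal at baseline, or above 3x baseline if elevated, with no upper limit. Bilirubin: "Normal TBL OR If TBL elevated at baseline : no change from baseline TBL". Action: "No change to study treatment", with repeat tests and monitoring but no SAE instruction.
- **Row 2.** ALT above 20x ULN. The bilirubin cell contains the single word *Normal*. Action: "Discontinue IV cipargamin and switch to IV artesunate", plus an SAE report. IV artesunate may continue on the investigator's benefit-risk assessment.
- **Row 3.** ALT above 3x ULN (or above 3x an elevated baseline), with total bilirubin at least 2x baseline and at least 2x ULN, "AND at least doubling of conjugated (=direct) bilirubin from baseline". Same actions as row 2.

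Rows 1 and 2 share the header "ALT increase without bilirubin increase post dose". Section 10.1.2 refers to Table 16-2 for protocol-specific hepatic SAEs, and Sections 6.2.1 and 9.1.1 refer to Section 16.1 for rescue and stopping on safety grounds.

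**The concern.** Row 1 spells out the alternative of a raised but unchanged bilirubin; row 2 does not. A site that applies the cells as written will therefore continue cipargamin, without an SAE report, in a participant with ALT above 20x ULN and raised bilirubin. It will stop cipargamin and report an SAE in a participant with the same ALT and normal bilirubin. The weaker instruction goes to the participant with the worse liver panel.

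The situation can arise. Only Cohort 1 excludes ALT above 5x ULN or bilirubin above 3 mg/dL (Section 5.2). In Cohorts 2-5, jaundice (bilirubin above 3 mg/dL with more than 100,000 parasites/µl) is itself a qualifying sign (Table 16-6). The absence of liver symptoms is realistic too. Section 4.5 says "Reversible and asymptomatic LFT elevations were observed with 75 mg single dose in a patient study in uncomplicated malaria", and also after 10 mg in a human challenge study, while noting that the disease or the challenge model may have contributed.

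At stake are the 24 h and 48 h cipargamin doses and the reporting of a hepatic SAE.

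**Working it through.** There is no plan figure to reproduce. The check is to apply the three rows to defined cases.

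**Inputs.** Row conditions come from Table 16-2; no liver symptoms. The documents give no ULN for bilirubin, so I assume 1.2 mg/dL, with a range of 1.0-1.3. *No change* is read as equality. For row 3, direct bilirubin is taken to have doubled as well.

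**Case A: ALT 25x ULN after dosing, baseline ALT normal or 4x ULN.** The row 1 ALT condition is met either way: 25 > 5, and 25/4 = 6.25 > 3. The matches are the same at every assumed ULN.

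| Baseline TBL (mg/dL) | Post-dose TBL | Rows matched now | With the core fix |
|---|---|---|---|
| 1.8 | 0.9 (normal) | 1 and 2 (2 is the higher tier: stop) | 2 |
| 1.8 | 1.8 (unchanged) | 1 only (continue) | 2 |
| 1.8 | 2.3 (risen, not doubled) | none | none, unless the optional line is added |
| 1.8 | 3.6 (doubled) | 3 (stop) | 3 |
| 3.1 | 3.1 (unchanged) | 1 only (continue) | 2 |
| 3.1 | 4.5 (risen, not doubled) | none | none, unless the optional line is added |
| 3.1 | 6.2 (doubled) | 3 (stop) | 3 |

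**Case B: baseline ALT 8x, rising to 22x ULN.** 22/8 = 2.75, which does not exceed 3, so row 1 is not met. Normal bilirubin matches row 2. Raised, unchanged bilirubin matches no row. In general, with raised static bilirubin, once baseline ALT exceeds 20/3 = 6.7x ULN, an ALT above 20x ULN but not above 3x baseline matches no row. A repaired row 2 must therefore not carry the 3x-baseline condition. Without it, both participants in Case B go to row 2.

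**Does another rule close the gap?**

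- *Hy's Law (Table 16-1).* This trigger is listed under normal baseline ALT, AST and total bilirubin, so a participant with raised baseline bilirubin is outside it as laid out. Even without that heading, it needs bilirubin of at least 2x ULN. A value of 1.8 mg/dL is 1.80, 1.50 or 1.38x ULN at ULN 1.0, 1.2 or 1.3, which is too low each time. A value of 3.1 mg/dL is 3.10, 2.58 or 2.38x ULN, so it would pass the bilirubin limit but still face the heading and the other conditions. The trigger makes the case an SAE (Section 10.1.2); it does not itself order a stop.
- *Sections 9.1.1, 10.2.1 and 6.2.1.* These require or allow stopping or rescue for a safety risk, where appropriate. Each depends on judgement, and 9.1.1 and 6.2.1 point back to Section 16.1.
- *Section 10.1.2.* The general criterion of medical significance allows an SAE report, again on judgement.

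**Timing.** Cipargamin is given at 0, 24 and 48 h (Table 6-2). Post-dose hepatic panels are scheduled at 12, 24, 36 and 48 h during that period (Tables 8-1 and 8-2). Only the second and third doses can be affected.

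**The case against.** The strongest reply is that the shared header settles the meaning. Both rows concern ALT rising without a bilirubin rise, row 1 explains what that includes, and row 2 is the higher ALT tier, so its cell is an abbreviation. That is probably what was intended, and it means the omission should not be read as a deliberate choice to continue dosing. It does not remove the problem: the action is attached to the cells, and the two cells differ.

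The second reply is that Table 16-2 does not act alone. Section 9.1.1 obliges the investigator to stop when continuing would harm the participant, Section 14.1 expects immediate safety action even as a deviation, and Section 10.1.2 allows any medically significant event to be reported as serious. This stands in part. A reader might infer that the protocol compels continued dosing in severe liver injury, or has no stop at all for such a participant. The documents do not support that. What is missing is the fixed stop and fixed SAE report that the same ALT triggers when bilirubin is normal.

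The third reply is that the case is narrow: bilirubin must be exactly unchanged, liver symptoms must be absent although Table 16-1 counts malaise, nausea and vomiting beside raised ALT, and the result must arrive before a remaining dose. This is fair and limits the weight of the point. A reader might also take Section 4.5 as evidence that cipargamin produces ALT above 20x ULN. It reports reversible elevations of uncertain cause and gives no such level.

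**Conclusion.** The point holds as an inconsistency in a stated safety rule. Without liver symptoms, and with bilirubin raised at baseline and unchanged, an ALT that rises after dosing above 20x ULN (from normal, or to more than 3x an elevated baseline) literally matches only the row that continues treatment. The same ALT with normal bilirubin is a stop and an SAE. The gap is foreseeable in Cohorts 2-5, affects at most two cipargamin doses per participant, and is cushioned by investigator judgement. The documents give no frequency, so no number of affected participants can be stated. The row matches rest on reading *no change* literally and on row 2 taking precedence where rows 1 and 2 overlap; they do not depend on the assumed bilirubin ULN within 1.0-1.3 mg/dL. The point merits correction because the repair is small and the rule concerns participant safety.

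**What to change.** Amend two rows of Table 16-2:

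1. Cap row 1 at ALT of 20x ULN or below.
2. Replace row 2's bilirubin cell with *normal, or, where raised at baseline, not increased since*. Apply row 2 to any post-dose ALT rise above 20x ULN, without a separate 3x-baseline condition. The shared header still fits.

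Optionally, add a line stating that ALT above 20x ULN with bilirubin increased but short of row 3 takes the same actions as rows 2 and 3. This goes beyond the inconsistency itself, but it covers the 2.3 and 4.5 mg/dL cases in the table above.

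The change needs no new test or visit. It may produce a few more switches to IV artesunate and a few more hepatic SAE reports. A switch counts as rescue (SAP Section 2.4.2) and, before 48 h, as not clinical success (Table 12-2). This can happen only in the cipargamin arms, because row 2 lets IV artesunate continue. The switch may also count toward the lack-of-efficacy criterion in Table 3-1, and a possibly related SAE toward the safety criterion, so one participant could add to both. The thresholds are 2 events in a cohort of 6 or 14, 3 in 20, 6 in 38 and 14 in 116. The sponsor should state whether a switch made for liver safety counts as lack of efficacy.

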16.2 Appendix 2: Specific Renal Alert Criteria and Actions and Event Follow-up

Table 16-3 Specific Renal Alert Criteria and Actions

Renal event	Actions
Confirmed serum creatinine increase 25 – 49%	
 Consider causes and possible interventions Follow-up within 24-48 h
Serum creatinine increase $\geq 50\%$ *OR if <18 years old , $\text{eGFR} \leq 35 \text{ ml/min/1.73 m}^2$	
 Consider causes and possible interventions Repeat assessment within 24-48h Consider drug discontinuation unless other causes are diagnosed and corrected Consider patient hospitalization and specialized treatment
New onset dipstick proteinuria $\geq 3+$	
 Consider causes and possible interventions Assess serum albumin & serum total protein Repeat assessment to confirm within 24-48h Consider drug discontinuation unless other causes are diagnosed and corrected
New onset hematuria $\geq 3+$ on urine dipstick	
 Repeat assessment to confirm within 24-48h Distinguish hemoglobinuria from hematuria Urine sediment microscopy Assess sCr Exclude infection, trauma, bleeding from the distal urinary tract/bladder, menstruation Consider bleeding disorder
+ Corresponds to KDIGO criteria for Acute Kidney Injury	

Follow-up of renal events:

Assess, document and record in CRF:

- Urine dipstick and sediment microscopy: crystals, red blood cells (dysmorphic/glomerular vs. non-dysmorphic/non-glomerular), white blood cells, tubular epithelial cells
- Blood pressure and body weight
- Serum creatinine, BUN, electrolytes (sodium, potassium, calcium) and bicarbonate
- Urine output

Whenever a renal event is identified, a detailed participant history and examination are indicated to identify and potentially eliminate risk factors that may have initiated or contributed to the event:

- Blood pressure assessment (after 5-minute rest)
- Signs and symptoms like fever, headache, shortness of breath, back or abdominal pain, dysuria or hematuria, dependent or periorbital edema
- Changes in blood pressure, body weight, fluid intake, voiding pattern, or urine output

- Concomitant events or procedures such as trauma, surgical procedures, cardiac or hepatic failure, contrast media or other known nephrotoxin administration, or other diseases or causes, e.g., dehydration due to delirium

Pediatric participants: special considerations

Schwartz formula:

- For **height in cm** and **SCr in mg/dL**: $\text{eGFR (ml/min/1.73 m}^2\text{)} = 0.413 \times (\text{height/SCr})$
- For **height in cm** and **SCr in $\mu\text{mol/L}$** : $\text{eGFR (ml/min/1.73 m}^2\text{)} = 36.5 \times (\text{height/SCr})$

Normal renal GFR values, as measured by inulin clearance ([Schwartz and Furth 2007](#)), are provided in [Table 16-4](#) below:

Table 16-4 **Normal GFR in children and young adults, as assessed by inulin clearance (adapted for pediatric participants included in this study)**

Age	Mean GFR \pm SD (ml/min per 1.73 m ²)
Term babies	
4-6 months	87.4 \pm 22.3
7-12 months	96.2 \pm 12.2
1-2 years	105.2 \pm 17.3
Children	
3-4 years	111.2 \pm 18.5
5-6 years	114.1 \pm 18.6
7-8 years	111.3 \pm 18.3
9-10 years	110.0 \pm 21.6
11-12 years	116.4 \pm 18.9
13-15 years	117.2 \pm 16.1
2.7-11.6 years	127.1 \pm 13.5
9-12 years	116.6 \pm 18.1
Young adults	
16.2-34 years	112 \pm 13

16.3

CCI

Table 16-5

CCI

CCI

16.4 Appendix 4: Modified version of WHO classification of signs of severe *P. falciparum* malaria

Severe malaria is defined as occurrence of one or more of the following observations, in the absence of an identified alternative cause, and in the presence of *P. falciparum* asexual parasitemia (WHO 2014)

Table 16-6 Definition of severe malaria

Signs	Definition
Impaired consciousness	A Glasgow Coma Score < 11 in adults or a Blantyre coma score < 3 in children
Prostration	Generalized weakness so that the person is unable to sit, stand or walk without assistance
Multiple convulsions	More than two episodes within 24 hours
Acidosis*	venous plasma lactate ≥ 4 mmol. Severe acidosis manifests clinically as respiratory distress – rapid, deep and laboured breathing
Hypoglycaemia	Blood or plasma glucose < 2.2 mmol (< 40 mg/dL)
Severe malarial anaemia	A haemoglobin concentration < 5 g/dl or a haematocrit of < 15% in children < 12 years of age (< 7 g/dl or < 20%, respectively, in adults) together with a parasite count > 10,000/ μ l
Renal impairment (acute kidney injury)**	Plasma or serum creatinine > 265 μ mol/L (3 mg/dL) or ≥ 3 x ULN or blood urea > 20 mmol/L
Jaundice	Plasma or serum bilirubin > 50 μ mol/L (3 mg/dL) with a parasite count > 100,000/ μ l
Pulmonary edema	Radiologically confirmed, or oxygen saturation < 92% on room air with a respiratory rate > 30/min, often with chest indrawing and crepitations on auscultation
Significant bleeding	Including recurrent or prolonged bleeding from nose gums or venepuncture sites; haematemesis or melaena
Shock	Compensated shock is defined as capillary refill ≥ 3 s or temperature gradient on leg (mid to proximal limb), but no hypotension. Decompensated shock is defined as systolic blood pressure < 70 mm Hg in children or < 80 mm Hg in adults with evidence of impaired perfusion (cool peripheries or prolonged capillary refill)
Hyperparasitemia	P. falciparum parasitemia > 10%
* Acidosis definition have been modified to categorize venous plasma lactate ≥ 4 mmol as acidosis .	
**Renal impairment definition have been modified to include Serum creatinine value of ≥ 3 ULN in the existing WHO definition	

